1 PROTOCOL SUMMARY

1.1 Protocol Synopsis

Sponsor: Ampio Pharmaceuticals, Inc.	Investigational Product: Ampion™
Title of Study: A Randomized, Double-Blinded, Placebo-Controlled Phase I Study to Evaluate the Safety and Efficacy of Ampion in Patients with Prolonged Respiratory Symptoms due to COVID-19 (Long-COVID)	
Rationale: The severe acute respiratory syndrome coronavirus 2 (SARS-CoV-2) has resulted in the pandemic spread of coronavirus disease 2019 (COVID-19), which has a high rate of infection, has a high rate of hospitalization, and has overwhelmed healthcare systems. Increasing numbers of people with COVID-19 are experiencing the lingering effects of COVID-19 and continue to have prolonged respiratory complications months after the onset of the disease, also known as Post-Acute Sequelae of SARS-CoV-2 (PASC), long-COVID, and/or long-hauler patients. The SARS-CoV-2 virus is transmitted through the respiratory system, which can cause a severe dysregulation of the immune response and damage in the lungs. Chronic, prolonged inflammation of the lungs maybe responsible for a myriad of continuing respiratory signs and symptoms post-infection, including cough, shortness of breath, chest discomfort, low exercise tolerance and low blood oxygen saturation. Ampion is the low molecular weight filtrate of human serum albumin with the in vitro ability to modulate inflammatory cytokine levels. Ampion has the potential to improve clinical outcomes for long-COVID patients. This study aims to evaluate the safety of Ampion and the clinical outcomes in patients with long-COVID. This is the first study for at-home use of Ampion inhaled treatment for long-COVID patients and will be used to inform decisions for the clinical development of Ampion.	
Lead Investigator(s): [name] MD	
Indication: Prolonged Respiratory Symptoms due to COVID-19 (Long-COVID)	
Number of Sites: Up to 5 sites	

Sponsor: Ampio Pharmaceuticals, Inc.	Investigational Product: Ampion™						
Number of Patients: Sample size is approximately 15 participants per treatment arm							
Treatment Groups: There are two planned treatment arms randomized 1:1, active to control:							


Treatment Arm	Investigational Treatment	

Active	Ampion Inhalation for 5-days	

Control	Placebo Inhalation for 5-days	

		Treatment Arm	Investigational Treatment	Active	Ampion Inhalation for 5-days	Control	Placebo Inhalation for 5-days
Treatment Arm	Investigational Treatment						
Active	Ampion Inhalation for 5-days						
Control	Placebo Inhalation for 5-days						
Objectives and Endpoints:							
Objective	Endpoint						
Primary							
Assess the effect of Ampion compared to placebo on safety	
Incidence and severity of adverse events (AEs) and serious adverse events (SAEs) from baseline to Day 28						
Exploratory							
Assess the effect of Ampion compared to placebo on symptom improvement	
Change in FDA Assessment of 14 Common COVID-19-Related Symptoms questionnaire from baseline to Day 7; Day 28; Day 60Change in Borg Dyspnoea Scale (mBDS) from baseline to Day 7; Day 28; Day 60Change in all-cause mortality						
Assess the effect of Ampion compared to placebo on pulmonary function	
Change in blood oxygen saturation from baseline to Day 7; Day 28; Day 60Change in six-minute walk test (6MWT) score from baseline to Day 7; Day 28; Day 60						
Assess the effect of Ampion compared to placebo on global impression	
Change in Quality-of-Life Assessment using SF-36 from baseline to Day 7; Day 28; Day 60Change in Fatigue questionnaire from baseline to Day 7; Day 28; Day 60Change in Sleep Disturbance questionnaire from baseline to Day 7; Day 28; Day 60						
Assess the effect of Ampion compared to placebo on radiographic findings	
Change in chest imaging on ground-glass opacity, local patchy shadowing, bilateral patchy shadowing, and/or interictal abnormalities from baseline to Day 60						

Study Design:

Overall Design

This is a Phase I randomized, double-blinded, placebo-controlled study in adult participants with prolonged respiratory symptoms due to COVID-19 (long-COVID).

Screening

Interested participants will sign the appropriate informed consent document(s) prior to completion of any study procedures. The investigator will review symptoms, risk factors and inclusion/exclusion criteria prior to any study procedures. If the participant is eligible and interested after this review, the participant will sign the appropriate informed consent document(s) prior to completion of any study procedures.

Double-Blind Treatment and Assessment

Participants will be randomized 1:1 to active treatment or placebo control using a random allocation sequence. Given the changing nature of the pandemic, periodic adjustments to the allocation ratio may be made in an effort to achieve equal allocation across the treatment arms at the end of the enrollment. There are two planned treatment arms:

Treatment Arm	Investigational Treatment
Active	Ampion Inhalation for 5-day
Control	Placebo Inhalation for 5-days

The general sequence of events during the treatment and assessment period:

- Complete baseline procedures and sample collection
- Participants are randomized to Ampion or placebo
- Participants receive study intervention (active or placebo) repeated daily for 5 days
- Complete safety monitoring and data collection
- Study visit types are described in the tables below:

Study Day	Visit Description	Visit Type
1	Baseline safety/efficacy measures	Conducted in outpatient clinic
1-5	Ampion inhalation treatment, safety measures	Conducted at home
7, 28, 60	Post-treatment safety/efficacy measures	Conducted in outpatient clinic

Post-Treatment Follow-up

Post-treatment follow-up will occur after Day 5 to assess clinical status and adverse events.

Disclosure Statement

This treatment study will be blinded to the investigator(s) and subject(s)

Data Safety Monitoring Board

There will be a Data Safety Monitoring Board (DSMB). Safety, including incidence of AEs/SAEs will be evaluated by a DSMB throughout the study.

Sponsor: Ampio Pharmaceuticals, Inc.	Investigational Product: Ampion™
Diagnosis and Main Criteria for Inclusion:	

1. Male or female adults: ≥ 18 years.2. Must have a clinical diagnosis of COVID-19 at least 4 weeks prior to the screening date, with at least one of clinical symptoms (e.g., fever $\geq 38^{\circ}\text{C}$, fatigue, cough) and a positive result by the reverse-transcription polymerase chain reaction (RT-PCR) testing or equivalent.3. Experiencing at least two COVID-19 respiratory symptoms with a score of two or higher using the FDA Assessment of 14 Common COVID-19-Related Symptoms questionnaire for at least 4 weeks (28 days) after initial positive COVID-19 diagnosis: cough, sore throat, runny/stuffy nose, shortness of breath (difficulties breathing), tightness of chest, low exercise tolerance.4. Able to bear weight and ambulate a minimum of 10 meters distance.5. Women of childbearing potential and their partner must agree to use at least one highly effective method of contraception (e.g., hormonal contraceptives [implants, injectables, combination oral contraceptives, transdermal patches, or contraceptive rings], intrauterine devices, bilateral tubal occlusion, or sexual abstinence) for the duration of the study.6. Informed consent obtained from the patient.	
Main Criteria for Exclusion:	

1. Subjects who require hospitalization.2. Patient has severe chronic obstructive or restrictive pulmonary disease (COPD) as defined by prior pulmonary function tests, chronic renal failure, or significant liver abnormality (e.g., cirrhosis, transplant, etc.).3. History of Chronic Fatigue Syndrome prior to COVID-19 infection.4. Patient is on chronic immunosuppressive medication.5. Patient requires surgery that could be life-threatening within the study window.6. A history of allergic reactions to human albumin (reaction to non-human albumin such as egg albumin is not an exclusion criterion) or ingredients in 5% human albumin (N-acetyl tryptophan, sodium caprylate).7. Patient has known pregnancy or is currently breastfeeding.8. Participation in a trial such that enrollment in this study would fall within the time frame of the half-life of the other investigational product(s).9. Clinically significant findings via electrocardiogram (ECG), including acute myocardial infarction, acute ischemic changes, atrial fibrillation, atrial flutter, paced rhythms in individuals who have undergone permanent pacemaker placement, evidence of prior infarction, unchanged stable conduction abnormalities e.g., right bundle branch block, or any other finding which does not significantly impact mortality.10. Pre-existing co-morbid condition(s) preventing outcome assessments, e.g. disease or condition that would prevent ability to transfer and walk for 6 minutes, prior to confirmed COVID-19 diagnosis (assisted walking devices are acceptable)	

Sponsor: Ampio Pharmaceuticals, Inc.	Investigational Product: Ampion™
11. As a result of the medical review and screening investigation, the Principal Investigator considers the patient unfit for the study.	
Test Product, Dose, and Mode of Administration: Participants in the active arm will inhale nebulized Ampion (8 mL) administered four times daily, every four to six hours, for 5 days. Nebulized drug will be delivered using the Aerogen Solo Nebulizer System with the Aerogen Solo Adaptor (FDA 510K K133360) manufactured by Aerogen Limited, Galway, Ireland. The Aerogen Solo Adaptor is a vibrating mesh nebulizer with a drug reservoir used for delivery of respiratory therapy, including the hand-held Aerogen Ultra. Medications will be recorded as concomitant medication, tabulated, and compared among groups.	
Reference Therapy, Dose and Mode of Administration: Participants in the control arm will inhale nebulized placebo (8 mL) administered four times daily for 5 days. Nebulized placebo will be delivered using the Aerogen Solo Nebulizer System with the Aerogen Solo Adaptor (FDA 510K K133360) manufactured by Aerogen Limited, Galway, Ireland. The Aerogen Solo Adaptor is a vibrating mesh nebulizer with a drug reservoir used for delivery of respiratory therapy, including the hand-held Aerogen Ultra. Medications will be recorded as concomitant medication, tabulated, and compared among groups.	
Study Duration: Treatment: 5 days Follow-up: 60 days	

1.2 Schedule of Assessments

Visits will be conducted as described:

Study Day ¹	Screening	Treatment					Post-Treatment Follow Up		
		1 ²	2	3 ²	4	5 ²	7	28	60
Visit Window (+/- # days)	--	--	--	--	--	--	3	3	3
COVID-19 tests	X								
Informed consent	X								
Medical history and pre-existing conditions	X								
Electrocardiogram (ECG)	X								
Pregnancy test	X								
Inclusion/exclusion criteria	X	X							
Demographics	X								
Randomization		X							
Treatment ^{1,2}		X	X	X	X	X			
Health check ^{1,2}		X		X		X			
Blood oxygen saturation		X					X	X	X
Assessment of 14 Common COVID-19-related symptoms questionnaire		X					X	X	X
Borg Dyspnoea Scale (mBDS)		X					X	X	X
Walk test		X					X	X	X
Chest x-ray imaging		X ³							X
Concomitant medications ²		X	X	X	X	X	X	X	X
Quality-of-Life Assessment SF-36		X					X	X	X
PROMIS Fatigue questionnaire		X					X	X	X
PROMIS Sleep Disturbance questionnaire		X					X	X	X
Adverse events ²		X	X	X	X	X	X	X	X

¹ Day 1, baseline assessments (health check, blood oxygen saturation, assessment of symptoms/questionnaires, mBDS, walk test, and chest x-ray) should occur before the first dose of treatment. These tests and the first dose of treatment will occur at the clinic. Treatment for the remainder of Day 1 and Days 2, 3, 4, 5 will occur at home.

² Day 1 post-first dose, Day 3 and Day 5 health check, concomitant medications and adverse event collection will occur via telephone visit.

³ Baseline chest x-ray may be performed after Screening, up to 3 days prior to Day 1.

TABLE OF CONTENTS

1	PROTOCOL SUMMARY	3
1.1	Protocol Synopsis.....	3
1.2	Schedule of Assessments	8
2	INTRODUCTION	13
2.1	Study Drug	13
2.2	Background to the Disease.....	14
2.3	Previous Human Experience.....	14
2.4	Study Rationale.....	15
2.4.1	Study Design.....	15
2.4.2	Study Background.....	15
2.4.3	Preclinical Data.....	16
2.4.4	Dosing Rationale.....	17
2.5	Benefit and Risk Assessment.....	17
3	STUDY DESIGN.....	18
3.1	Study Design Overview	18
3.2	Study Objectives	18
3.2.1	Primary Objective	18
3.2.2	Secondary Objectives.....	18
3.3	Study Endpoints	18
3.3.1	Primary Endpoint	18
3.3.2	Exploratory Endpoints	18
3.4	Blinding and Randomization	19
3.5	Data Safety Monitoring Board.....	20
3.6	Stopping rules	20
4	SELECTION OF PARTICIPANTS	21
4.1	Number of Participants	21
4.2	Recruitment Methods.....	21
4.3	Participant Characteristics	21
4.4	Inclusion Criteria	21
4.5	Exclusion Criteria	22
5	STUDY PLAN, PROCEDURES, AND ASSESSMENTS	23
5.1	Study Plan	23

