5.2 Description of Study Visits

The Schedule of Assessments is shown in [Section 1.2](#). Visit types are described as follows:

Study Day	Visit Description	Visit Type
1	Baseline safety/efficacy measures	Conducted in outpatient clinic
1-5	Ampion inhalation treatment, safety measures	Conducted at home
7, 28, 60	Post-treatment safety/efficacy measures	Conducted in outpatient clinic

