5.2.4 Post Treatment Follow Up (Day 7)

The following procedures will be performed at Day 7 (endpoint):

- Blood oxygen saturation
- Assessment of 14 Common COVID-19-related symptoms questionnaire
- Borg Dyspnoea Scale and walk test.
- Record concomitant medications/therapies
- Quality-of-life assessment SF-36
- PROMIS fatigue and PROMIS sleep disturbance questionnaires
- Record adverse events

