7.1 Dosing and Administration of Study Medication

Study treatment (Ampion or placebo) will be provided as a solution in vials ready for human use and treatment administration. The participant will be trained to self-administer the study treatment. Treatment should start within 24 hours of randomization and should terminate on last treatment day (Day 5).

Study treatment (Ampion or placebo) will be delivered by inhalation using a nebulizer as a 32mL daily dose administered four times daily (8mL per treatment) every four to six hours for five days.

Study treatment (Ampion or placebo) is presented as a sterile liquid in a glass vial. For each use, the contents of are transferred to the drug reservoir in the nebulizer and nebulized continuously until the drug is fully administered.

Study treatment (Ampion or placebo) is aerosolized for inhalation using the Aerogen Ultra handheld nebulizer (Aerogen Limited, Galway, Ireland, FDA 510K K133360), which consists of the Aerogen Pro-X Controller and the Aerogen Ultra handheld unit. The system is a portable medical device for single patient use indicated for aerosolization of physician-prescribed solutions for inhalation. Ampion is nebulized using the continuous setting on the Aerogen controller, and the study drug is nebulized until it is fully aerosolized.

Product administration may be temporarily suspended until resolution if a serious, or sudden side effects are observed. The nature of the event will be evaluated (i.e., allergic; localized; systemic or otherwise) and appropriate measures applied, which may include symptomatic treatment with antihistamines and antiallergic measures, paracetamol (acetaminophen) and/or corticosteroids.

As described in [Section 6.1](#), if any reactions of grade 3 and above (as defined using the CTCAE grading scale version 5.0 or newer) are observed in any patient within 24 hours of product administration, a safety investigation will occur, which may trigger the temporary suspension of study product administration.

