14 SCHEDULE OF EVENTS

	Screen	Treatment					Post-Treatment Follow-Up		
		1 ²	2	3 ²	4	5 ²	7	28	60
Study Day	-3 to 1								
Visit Window (± days)	--	--	--	--	--	--	3	3	3
COVID-19 tests	X								
Informed consent	X								
Medical history and pre-existing conditions	X								
Electrocardiogram (ECG)	X								
Pregnancy test	X								
Inclusion/exclusion criteria	X	X							
Demographics	X								
Randomization		X							
Treatment ^{1,2}		X	X	X	X	X			
Health check		X		X		X			
Blood oxygen saturation		X					X	X	X
Assessment of 14 Common COVID-19-Related symptoms questionnaire		X					X	X	X
Borg Dyspnoea Scale (mBDS)		X					X	X	X
Walk test		X					X	X	X
Chest x-ray imaging		X ³							X
Concomitant medications ²		X	X	X	X	X	X	X	X
Quality of Life Assessment (SF-36)		X					X	X	X
PROMIS Fatigue questionnaire		X					X	X	X
PROMIS Sleep Disturbance questionnaire		X					X	X	X
Adverse events ²		X	X	X	X	X	X	X	X

¹ Day 1, baseline assessments (health check, blood oxygen saturation, assessment of symptoms/questionnaires, mBDS, walk test, and chest x-ray) should occur before the first dose of treatment. These tests and the first dose of treatment will occur at the clinic. Treatment for the remainder of Day 1 and Days 2, 3, 4, 5 will occur at home.

² Day 1 post-first dose, Day 3 and Day 5 health check, concomitant medications and adverse event collection will occur via telephone visit.

³ Baseline chest x-ray may be performed after Screening, up to 3 days prior to Day 1.

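### The Day 7 visit window reaches back to Days 4 and 5, inside the dosing period, and contradicts the protocol's statement that post-treatment follow-up comes after Day 5

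*Protocol*

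**What the plan says.** Protocol section 1.2 has a row headed "Visit Window (+/- # days" with 3 entered under each of Days 7, 28 and 60. SAP section 14 has the same entries under "Visit Window (± days". No footnote in either table shortens the Day 7 window on its early side.

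The same tables mark treatment on Days 1 to 5. A protocol footnote says "Treatment for the remainder of Day 1 and Days 2, 3, 4, 5 will occur at home". Protocol section 7.1 gives the regimen as a "32mL daily dose administered four times daily (8mL per treatment) every four to six hours for five days" and adds: "Treatment should start within 24 hours of randomization and should terminate on last treatment day (Day 5".

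Other text treats Day 7 as a visit made once dosing is over:

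- The synopsis says "Post-treatment follow-up will occur after Day 5 to assess clinical status and adverse events".
- Protocol section 5.2 describes the Day 7, 28 and 60 visits as "Post-treatment safety/efficacy measures".
- Protocol section 5.2.4, whose heading is post-treatment follow-up, opens its list with "The following procedures will be performed at Day 7 (endpoint".

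SAP sections 5.2.1 to 5.2.3 test percent change from baseline at Day 7 with a Wilcoxon rank-sum test. The SAP does not define analysis-visit windows, and it has no rule for an assessment made before a participant's last dose.

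**The concern.** A site that books the Day 7 visit on Day 4 or Day 5 complies with the printed window, yet the participant may still have doses to take. The assessment would then enter the analysis as a post-treatment value, alongside values taken up to five days after dosing ended.

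Such a value reflects an incomplete course and any immediate effect of nebulisation. The symptom questionnaire is the most exposed, because its severity items ask for the worst level over the preceding 24 hours (Protocol section 5.3; SAP section 15.1). On Day 4 or 5 that recall period falls on dosing days. The questionnaire also stands first in the hierarchical testing order of SAP section 5.2. At stake is what the Day 7 comparison estimates: the effect after a full course, or a mixture of that and the state during dosing.

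**Working it through.** The documents do not print the resulting range of days, so there is no figure of theirs to reproduce. The check is interval arithmetic.

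**Inputs.** Nominal visit days 7, 28 and 60, each with a 3-day window on both sides (Protocol section 1.2; SAP section 14). Dosing on Days 1 to 5, four times daily (Protocol sections 1.2 and 7.1).

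**Step 1: permitted days against dosing days.**

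| Visit | Permitted days | Overlap with Days 1 to 5 |
|---|---|---|
| Day 7 | 7 - 3 = 4 to 7 + 3 = 10 | Days 4 and 5 |
| Day 28 | 28 - 3 = 25 to 28 + 3 = 31 | none |
| Day 60 | 60 - 3 = 57 to 60 + 3 = 63 | none |

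Two of the seven permitted days for the Day 7 visit are dosing days.

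**Step 2: how much of the course is complete.** Planned doses: 4 per day x 5 days = 20. A visit on Day d follows between 4 x (d - 1) and 4 x d doses.

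- Day 4: 12 to 16 of 20, or 60% to 80%. The course is never complete.
- Day 5: 16 to 20 of 20, or 80% to 100%. It is complete only if the visit follows the last dose.

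These counts assume four doses on every day from Day 1.

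**Step 3: is a Day 5 visit usually before the last dose?** Four doses at intervals of four to six hours span 3 x 4 = 12 to 3 x 6 = 18 hours. If the first Day 5 dose is at 07:00 (an assumption), the fourth falls between 19:00 and 01:00. A visit in ordinary clinic hours would then come before it.

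**Step 4: later start.** Protocol section 7.1 allows treatment to begin up to 24 hours after randomisation. If the first dose fell on the next calendar day and all five days were given (an assumption, since the same section ends treatment on Day 5), dosing would run on Days 2 to 6. The overlap would then be Days 4, 5 and 6.

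**Step 5: endpoints affected.** Protocol section 3.3.2 lists nine exploratory endpoints. Seven have a Day 7 value: symptom questionnaire, Borg scale, oxygen saturation, six-minute walk, SF-36, PROMIS fatigue and PROMIS sleep disturbance. Mortality is compared over 60 days (SAP section 5.2.1), and chest imaging is assessed only at Day 60 (SAP section 5.2.4).

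**Step 6: what lower limit agrees with the synopsis.** With the upper limit kept at +3, a lower limit of -3 gives Days 4 to 10, -2 gives Days 5 to 10, and -1 gives Days 6 to 10. If dosing is on Days 1 to 5, only -1 or tighter removes the overlap.

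**The case against.** The strongest reply is that the protocol, read as a whole, already answers the point. The synopsis puts follow-up after Day 5, the Day 7 column sits under a post-treatment heading, home dosing fills Days 1 to 5, and Day 5 has its own telephone contact. On that reading the working window is Days 6 to 10 and the table cell was simply not trimmed. This shows what was probably intended, so the point is an inconsistency to reconcile. It does not remove the problem: the synopsis sentence appears in neither schedule, nor in Protocol section 5.2.4 or the SAP, and compliance will be judged from the window row.

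The limits on importance also stand. The study is not powered (Protocol section 4.1), the affected endpoints are exploratory, and Protocol section 9.4.2 plans only descriptive statistics for them.

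A reader might infer more than the documents support:

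- **That all efficacy endpoints are touched.** Two of the nine have no Day 7 value.
- **That 2/7, or 29%, of visits would be early.** That is a share of calendar days. Nothing suggests that visits spread evenly over the window.
- **That one arm is favoured.** Both blinded arms have the same window, and nothing shows that early visits would differ between them.
- **That the interim analysis rests on these values.** Protocol section 9.2.3 sets the interim at Day 7 completion, but SAP section 6.1 sets it at Day 28. That is a separate conflict, and it leaves the interim argument unsettled.

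**Conclusion.** The point holds as a contradiction between the printed Day 7 window and the protocol's own description of the visit. As written, a Day 4 visit, or a Day 5 visit before the last dose, is in window and would be analysed as the post-treatment Day 7 value for seven exploratory endpoints.

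The size is modest. The likely effect is dilution or added noise at one exploratory timepoint. The primary adverse event endpoint does not depend on this window, and the Day 28 and Day 60 windows lie well clear of dosing. The documents do not allow the number of early visits to be estimated.

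The conclusion rests on dosing taking place on Days 1 to 5 as the schedules show. A later start would widen the overlap by a day. It should be corrected because the inconsistency is plain and the remedy is cheap, but it does not threaten the trial's main conclusion.

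**What to change.** **Both schedules.** Reconcile the Day 7 window with the synopsis, for example as -1/+3 (Days 6 to 10). State also that the visit must follow the participant's last dose, because the 24-hour start allowance could move dosing so that a Day 6 opening alone would not ensure it. A Day 6 visit agrees with the synopsis, although its 24-hour symptom recall still reaches back into Day 5.

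**SAP.** Keep all values in the main Day 7 analysis, in line with the ITT definition in section 6.2.2. Add a listing of assessment date and time against last dose, and a sensitivity summary that leaves out assessments made before the last dose. Excluding them from the main analysis is not advised: it would drop randomised participants' data on a post-randomisation criterion, with about 15 per arm and no imputation rule for efficacy data. An exclusion by date alone would also discard Day 5 visits made after the final dose.

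**Cost.** Slightly less scheduling freedom, a protocol amendment with the approvals required by Protocol section 10.3, and a short SAP addition settled before unblinding. The sponsor should confirm that clock times of the last dose and of the visit are captured, since the documents do not say so.

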3.2 Study Objectives

3.2.1 Primary Objective

The primary trial objective is to evaluate the safety and tolerability of inhaled Ampion versus placebo control in adult participants with prolonged respiratory complications after COVID-19 infection.

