5.3 Assessment Methods

Demographic Data

Demographic data will be collected: age, gender, race, height and weight, comorbidities.

Health Check

A health check will be conducted at the clinic at baseline to include the measurement of vital signs (i.e., heart rate, blood pressure, respiratory rate, temperature). A general health check will be conducted Day 1 post-first dose, Day 3, and Day 5 via telephone visit.

Blood Oxygen Saturation (SpO2)

SpO2 will be collected at baseline and Days 7, 28, and 60 using a pulse-oxygen measuring device.

Assessment of 14 Common COVID-19-related symptoms questionnaire

The FDA assessment of 14 Common COVID-19- related symptoms questionnaire will be conducted at baseline, Day 7, Day 28, and Day 60 as follows:

Example items For items 1–10, sample item wording could be: “What was the severity of your [insert symptom] at its worst over the last 24 hours?”	Example response options and scoring*
1. Stuffy or runny nose	
2. Sore throat	
3. Shortness of breath (difficulty breathing)	
4. Cough	None = 0
5. Low energy or tiredness	Mild = 1
6. Muscle or body aches	Moderate = 2
7. Headache	Severe = 3
8. Chills or shivering	
9. Feeling hot or feverish	
10. Nausea (feeling like you wanted to throw up)	
11. How many times did you vomit (throw up) in the last 24 hours **	I did not vomit at all = 0 1–2 times = 1 3–4 times = 2 5 or more times = 3

continued

Table 1, continued

12. How many times did you have diarrhea (loose or watery stools) in the last 24 hours ??	I did not have diarrhea at all = 0 1–2 times = 1 3–4 times = 2 5 or more times = 3
13. Rate your sense of smell in the last 24 hours	My sense of smell is THE SAME AS usual = 0 My sense of smell is LESS THAN usual = 1 I have NO sense of smell = 2
14. Rate your sense of taste in the last 24 hours	My sense of taste is THE SAME AS usual = 0 My sense of taste is LESS THAN usual = 1 I have NO sense of taste = 2

* Note: Score values are included in the table for ease of reference. FDA cautions against including the score values within the response options presented to trial subjects to avoid confusing subjects.

** The response options shown for items 11 and 12 are intended only for use with a 24-hour recall period.

Time to Sustained Recovery

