The time to sustained recovery will be evaluated using the FDA Assessment of 14 Common COVID-19-Related Symptoms questionnaire. Time to sustained recovery is defined as the first day on which the patient achieves a state of ‘none’ or ‘0’ using the FDA assessment.

Borg Dyspnoea Scale

Borg Dyspnoea Scale will be conducted at baseline, Day 7, Day 28, and Day 60. This scale asks you to rate the difficulty of your breathing it starts at number 0 where you are breathing is causing you no difficulty at all and progresses through to number 10 where your breathing difficulty is maximal.

Walk Test

A six-minute walk test will be conducted at baseline, Day 7, Day 28, and Day 60. The walk test is conducted as follows:

- Flat, straight corridor 30 m (100 feet) in length
- Turnaround points marked with a cone
- Patient should wear comfortable clothes and shoes
- Patient rests in chair for at least 10 minutes prior to test (ie, no warm-up period)

- Heart rate and pulse oxygen saturation (SpO₂) should be monitored throughout the test
- If the patient is using supplemental oxygen, record the flow rate and type of device
- Have patient stand and rate baseline dyspnea and overall fatigue using Borg scale*^[1]
- Set lap counter to zero and timer to six minutes
- Instruct the patient: Remember that the object is to walk AS FAR AS POSSIBLE for 6 minutes, but don't run or jog. Pivot briskly around the cone.
- Standardized encouragement statements should be provided at one-minute intervals, such as "You are doing well. You have _ minutes to go" and "Keep up the good work. You have _ minutes to go."
- At the end of the test, mark the spot where the patient stopped on the floor
- If using a pulse oximeter, measure the pulse rate and SpO₂ and record
- After the test record the Borg*^[1] dyspnea and fatigue levels
- Ask, "What, if anything, kept you from walking farther?"
- Calculate the distance walked and record

1. *Borg GA. Psychophysical bases of perceived exertion. Med Sci Sports Exerc 1982; 14:377.*
2. *American Thoracic Society. ATS statement: Guidelines for the six-minute walk test. Am J Respir Crit Care Med 2002; 166:111.*

Chest X-Ray Imaging

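### No structured symptom score is scheduled between the first dose and Day 7, so mild-to-moderate transient worsening of existing respiratory symptoms during dosing may be under-recorded or recorded unevenly

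*Protocol*

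**What the plan says.** Protocol 3.2.1 sets the primary objective: to "evaluate the safety and tolerability of inhaled Ampion versus placebo control in adult participants" with prolonged respiratory complications. Inclusion criterion 3 (Protocol 1.1 and 4.4) requires "Experiencing at least two COVID-19 respiratory symptoms with a score of two or higher" on the FDA 14-symptom questionnaire.

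For the scored measures, Protocol 5.3 says:
- the "symptoms questionnaire will be conducted at baseline, Day 7, Day 28, and Day 60 as follows", with severity items asking about the symptom "at its worst over the last 24 hours";
- "Borg Dyspnoea Scale will be conducted at baseline, Day 7, Day 28, and Day 60";
- "SpO2 will be collected at baseline and Days 7, 28, and 60 using a pulse-oxygen measuring device".

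Footnote 1 to Protocol 1.2 puts the Day 1 measures before the first dose. SAP section 14 repeats the same schedule.

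For the dosing days, footnote 2 to Protocol 1.2 says: "Day 1 post-first dose, Day 3 and Day 5 health check, concomitant medications and adverse event collection will occur via telephone visit". Protocol 5.3 adds: "A general health check will be conducted Day 1 post-first dose, Day 3, and Day 5 via telephone visit". Protocol 5.2.3 also allows text message. Beyond vital signs at the clinic baseline, no content is listed for the health check.

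**The concern.** Short-lived airway irritation is the most direct tolerability question for a nebulised product. Here it would arise in people who already cough or are breathless, so a modest increase after a dose is easily put down to long-COVID. Protocol 8.1 does not say how much worsening of an existing symptom makes an adverse event. Without a score to compare with the pre-dose value, the decision rests on the judgement of the participant and the caller, at up to 5 sites. A finding of similar tolerability in the two arms could then partly reflect what was not measured, and Day 1-5 data cannot be collected afterwards.

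**Working it through.** The plan states no figure that bears on this point. Protocol 4.1 gives 15 per arm and says the study is not powered. The check is a reading of the schedule, followed by an illustration on assumed rates.

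**Schedule against dosing days**
- Inhalations (Protocol 7.1): 4 per day x 5 days = 20. The first is in clinic (Protocol 1.2, footnote 1), so 20 - 1 = 19 are at home.
- Contacts during dosing: Day 1 after the first dose, Day 3 and Day 5, which is 3.
- Symptom questionnaire, Borg scale or SpO2 scheduled after the first dose and up to Day 5: 0.
- Recall at the nominal Day 7 visit: the preceding 24 hours, so Days 6-7. The last dosing day is Day 5. Dosing days covered: 0 of 5.
- Visit window: 7 - 3 = Day 4 to 7 + 3 = Day 10. A visit held on Day 4 or 5 would fall in the dosing period, and one on Day 6 would reach back into Day 5. That happens only by chance of scheduling.
- Room to worsen: items 1-10 run from 0 to 3. A symptom entering at 2 can rise by 3 - 2 = 1 category; one entering at 3 cannot rise.

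**Illustration (assumptions)**

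The documents give neither the rate of inhalation-provoked worsening nor the share recorded. Take A ~ Binomial(15, p_A x c) and B ~ Binomial(15, p_B x c), independent, where c is the share captured, and compute P(A - B >= 3). This threshold is not a rule in the plan.

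The noise column takes full capture by scoring but adds chance rises. With 4 items at 2 calls there are 8 comparisons. If each rises by chance 5% of the time, independently, the background is b = 1 - 0.95^8 = 34%, and each arm's rate becomes 1 - (1 - p)(1 - b).

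| True rates, Ampion v placebo | c = 100% | c = 50% | c = 100% with 34% background, any item |
|---|---|---|---|
| 40% v 10% | 82% | 43% | 58% |
| 30% v 10% | 59% | 26% | 43% |
| 20% v 10% | 30% | 11% | 29% |

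Two things follow. Lower capture hides a difference at every pair of rates, but the size of the loss depends on inputs that the plan does not supply. And counting a rise on any item is a noisy summary. With three calls there are 12 comparisons, background is 1 - 0.95^12 = 46%, and the 40% v 10% case falls to 49%. For a single item over three calls the background is 1 - 0.95^3 = 14%, which favours a per-item display.

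Sample size limits the answer in any case: with 0 of 15 recorded and perfect capture, the one-sided 95% upper bound on the true rate is 1 - 0.05^(1/15) = 18%.

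**The case against.** The strongest reply is that on-treatment safety is collected, and by active contact. Footnote 2 schedules adverse-event collection at three calls, and the schedule marks adverse events on every dosing day. A reader might infer that reporting on Days 1-5 is unsolicited. The documents do not support that: Protocol 8.3 names spontaneous report as one possible source and does not bar asking, and the call script is not in the documents.

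A reader might also infer that any worsening provoked by inhalation could pass unseen. That is too broad. The first dose is in clinic. Grade 3 or higher nebulization reactions within 24 hours lead to a safety investigation (Protocol 6.1 and 7.1), and a severe local reaction goes to the DSMB at once. Concomitant medication and exposure are recorded. These safeguards stand, with one qualification: the suspension trigger based on vital signs (Protocol 6.1) and the vital-sign summaries over time (SAP 8.4) sit beside a protocol that specifies a full vital-sign set only at the clinic baseline. Those passages must be reconciled.

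The rule that incomplete adverse-event data take the greatest relationship or severity (Protocol 9.5) helps only once an event has been recorded.

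It is also fair that a 30-participant Phase I trial can rest tolerability on adverse events alone. What survives is narrow: no structured score exists for mild-to-moderate, transient worsening of a symptom already present.

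**Conclusion.** The point holds in this limited form, as a cheap improvement and not as an error in the plan. Its firm size is 0 scored symptom assessments scheduled from the first dose through Day 5, and 0 of 5 dosing days inside the recall of a nominal Day 7 visit. Neither figure needs an assumption.

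That such worsening may be under-recorded, or recorded unevenly between sites, is a reasoned inference from the symptomatic population, the unspecified content of the calls and the absence of a rule for worsening over baseline. No numerical loss of detection should be claimed. A single pair of rates, such as 40% v 10%, makes the loss look large and the remedy complete. At 20% v 10% the chance of seeing an excess of 3 is only 30% with full capture, and chance rises erode the gain from scoring.

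**What to change.** In Protocol 1.2 and 5.3, add questionnaire items 1-4 (runny nose, sore throat, shortness of breath, cough) to the three calls already scheduled. Word the Day 1 post-dose call as since the first dose, so that pre-dose hours are excluded. Keep the 24-hour recall at Day 3 and Day 5, which then covers Days 2-3 and 4-5. Use the same wording if the contact is by text message.

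In SAP section 8, add a descriptive by-arm Day 1-5 tolerability table. For each item it should show the change from the Day 1 pre-dose score and the number of participants with any rise, with those already at 3 shown separately because they cannot rise.

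Leave adverse-event determination to the existing definition in Protocol 8.1. A rule turning every one-category rise into an adverse event would alter the primary endpoint, which is adverse-event incidence and severity.

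Cost: about 2 minutes per call, one eCRF page and one table, with no new contact or visit. Chance rises will appear in both arms, which is why the table compares arms, and prompting may bring a few more mild adverse-event reports. Limits: chest tightness and low exercise tolerance qualify a participant but are not questionnaire items, and the hours between the Day 1 call and Day 2, and after the Day 5 call, stay unscored.
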